1 OBJECTIVES

1.1 Primary Objectives

- 1.1.1 To evaluate the feasibility of [¹⁴C]oxaliplatin microdose as a clinical assay to predict oxaliplatin exposure

1.2 Secondary Objectives

- 1.2.1 To estimate the degree to which a [¹⁴C]oxaliplatin microdose predicts the observed pharmacokinetics of standard dose oxaliplatin
- 1.2.2 To validate that intrapatient variation of exposure to a [¹⁴C]oxaliplatin microdose is less than 5%
- 1.2.3 To detect the levels of oxaliplatin-DNA adducts induced by oxaliplatin microdosing in peripheral blood mononuclear cells (PBMC), and correlate the results with patient response and progression free survival on oxaliplatin-based chemotherapy
- 1.2.4 To develop preliminary safety data of [¹⁴C]oxaliplatin microdosing for future studies

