6 STUDY DESIGN AND TREATMENT PLAN

6.1 Study Design

This is a prospective feasibility study of a [¹⁴C]oxaliplatin microdose assay to predict exposure and sensitivity to oxaliplatin as part of standard-of-care FOLFOX chemotherapy. Consenting patients who will be receiving FOLFOX as their treatment for cancer will be enrolled. Patients will receive two [¹⁴C]oxaliplatin microdose infusions over the course of the study. The first part of the study is a Phase 0 [¹⁴C]oxaliplatin microdose infusion occurring over 2 hours and followed by serial blood draws over a 24 hour period for microdose pharmacokinetic and pharmacodynamic analysis (on surrogate peripheral blood mononuclear cells). Between 2 days and 4 weeks after the administration of this phase 0 microdose, patients will begin FOLFOX therapy according to usual care. The initial treatment oxaliplatin dose will be diluted with the same amount of [¹⁴C]oxaliplatin microdose as previously administered. Repeat blood draws for pharmacokinetic assessment of both the microdose and therapeutic dose along with pharmacodynamic analysis on PBMCs will be performed over 46-48 hours (this last draw is timed for the disconnect visit of the 5-FU infusion).

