6.3 Phase 0 [¹⁴C]Oxaliplatin Microdose

6.3.1 Preparation and Administration of [¹⁴C]Oxaliplatin Microdose

The starting dose (Dose Level 1, **Table 1**) of [¹⁴C]oxaliplatin microdose to be administered in this study is 2×10^6 dpm/kg of body weight, with the total dose of both unlabeled and ¹⁴C-labeled oxaliplatin solution being 1/100th of the planned therapeutic dosage (85 mg/m²). Calculations of the therapeutic dose and microdose of oxaliplatin will use the Du Bois and Du Bois formula for BSA:

$$\text{BSA (m}^2\text{)} = 0.20247 \times \text{Height(m)}0.725 \times \text{Weight(kg)}0.425$$

The dose of [¹⁴C]oxaliplatin is calculated in the following formula using Dose Level 1 (2 X 10⁶ dpm/kg, 1% therapeutic dose):

$$2 \times 10^6 \text{ dpm/kg} \div (2.22 \times 10^9 \text{ dpm/mCi}) \div 54 \text{ mCi/mmol} \times 397 \text{ mg/mmol} = 0.0066 \text{ mg/kg}$$

The patient specific dose of [¹⁴C]oxaliplatin will be added to an infusion bag containing D5W. Unlabeled oxaliplatin will be added to a separate infusion bag also containing D5W. Both treatment dose of unlabeled oxaliplatin and ¹⁴C-labeled oxaliplatin will be concurrently infused intravenously over 2 hours at the UC Davis Cancer Center Infusion Center. When these two infusion bags are concurrently administered to a patient, together they achieve a total final oxaliplatin microdose of 1% of the therapeutic dose. A chemotherapy nurse will administer the unlabeled oxaliplatin. A Nuclear Medicine Technologist (CNMT) will administer the ¹⁴C-labeled oxaliplatin via Y-site connection to the unlabeled oxaliplatin.

As an example, a patient with a height of 1.7 m and a body weight of 75 kg will have a BSA of 1.86 m². This patient would be planned to receive a therapeutic oxaliplatin dose of 158 mg (85 x 1.86). This patient's microdose would then be 1.58 mg of total oxaliplatin containing 1.08 mg of unlabeled oxaliplatin for injection and 0.50 mg [¹⁴C]oxaliplatin solution. The above dosing calculation should be modified as appropriate for the other dose levels in **Table 1**. [name], [name] or their designees are the only authorized prescribers for the microdosing formulation. If the designee signs the pharmacy order form in [name] or [name] absence, the designee must notify [name] or [name] as soon as possible before dosing the patient.

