6.5.2 FOLFOX

Patients will be treated with modified FOLFOX6 according to the following initial schedule for cycle 1. Cycle length is defined as 14 days. Modifications to cycle 1 treatment (other than oxaliplatin dose) may be allowed, but discussion with the primary investigator is required. Modifications to dosing beyond cycle 1 are at the discretion of the treating investigator according to usual medical practice.

Table 4. Modified FOLFOX6 Chemotherapy Regimen

Agent	Dose	Route	Day	Schedule
Leucovorin	400 mg/m ²	IV	1	Every 14 days
Calcium*				
5-FU	400 mg/m ²	Bolus IV	1	Every 14 days
Oxaliplatin	85 mg/m ²	IV over 2 hours	1	Every 14 days
5-FU	2400 mg/m ²	IV over 46-48 hours via ambulatory infusion pump	1-2	Every 14 days

*In the event of a leucovorin calcium shortage, the dosage may be reduced to 20 mg/m² or 200 mg/m² racemic levoleucovorin may be substituted. Leucovorin may be infused concurrently with oxaliplatin (via separate infusion lines).

** Note during cycle 1 only, Oxaliplatin infusion will contain [¹⁴C]Oxaliplatin Microdose as described in section 6.4.1

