8.2.2 Secondary Endpoints

Secondary endpoints include:

- 8.2.2.1 Assessment of other PK parameters (e.g. C_{max} , t_{max} , $t_{1/2}$, CL) of the phase 0 microdose compared to the therapeutic dose.
- 8.2.2.2 Comparison of the PK parameters of the phase 0 microdose to the FOLFOX-integrated microdose.
- 8.2.2.3 The association of oxaliplatin-DNA adducts (see **section 10.3**) and tumor response by RECIST 1.1 (see **Appendix C**).
- 8.2.2.4 The association of oxaliplatin-DNA adducts (see **section 10.3**) and duration of disease control (see **Appendix C**).
- 8.2.2.5 Safety according to the Common Terminology Criteria for Adverse Events version 4 (see **section 7.2**).

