11.2.2 Secondary Analyses

Given the small number of patients included in this pilot study, all secondary analyses will be considered hypothesis generating for the design of future confirmatory study.

11.2.2.1 For secondary endpoint 8.2.2.1, we will correlate PK parameters from microdosing with parameters from therapeutic doses of oxaliplatin. All parameters will be normalized for dose. We will present descriptive summaries (scatterplots, tables, mean, SD,

correlation coefficient) of the relationship between the two sets of parameters.

11.2.2.2 For secondary endpoint 8.2.2.2, we will correlate PK parameters from phase 0 microdosing with parameters from FOLFOX-integrated microdosing of oxaliplatin. We will present descriptive summaries (scatterplots, tables, mean, SD, correlation coefficient) of the relationship between the two sets of parameters.

11.2.2.3 For secondary endpoint 8.2.2.3 and 8.2.2.4, we will characterize the repair of DNA adducts in PBMC, using descriptive statistics (graphical summaries, mean, SD, box plots). Response rate and duration of disease control (DDC) will be measured according to RECIST 1.1 (**Appendix C**). The DDC is equivalent to progression free survival if an intermittent oxaliplatin strategy is not employed. Progression free survival will be calculated from the date of enrollment to the date of first objective evidence of radiographic progression (soft tissue or bone lesion) or date of death due to any cause, whichever occurs first. If an intermittent oxaliplatin strategy is chosen, we will define DDC as the addition of the initial PFS and the PFS of the reintroduction, except in case of progression at the first evaluation after FOLFOX reintroduction. Radiological assessment by the treating Investigator will be the primary report in this analysis. We hypothesize that higher levels of DNA repair will be associated with non-response and shorter duration of disease control.

11.2.2.4 For secondary endpoint 8.2.2.5, we will assess toxicity to both micordoses of [¹⁴C]oxaliplatin. Toxicities potentially related to [¹⁴C]oxaliplatin will be assessed from initiation of the study to at least 14 days after the administration of the FOLFOX-integrated microdose or until full recover of toxicity (whichever is longer). Safety will be assessed through summaries of adverse events and laboratory evaluations. Descriptive statistics will be used rather than inferential statistics.

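### Objective 1.2.2, validating intrapatient variation of microdose exposure below 5%, is not supported by a design in which the second labelled dose is given within the therapeutic dose

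*Combined protocol and SAP*

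**What the plan says.** Section 1.2 lists as objective 1.2.2: "To validate that intrapatient variation of exposure to a [¹⁴C]oxaliplatin microdose is less than 5"%. Section 2 counts intrapatient variability of microdose pharmacokinetics among the key secondary objectives.

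Section 6.1 fixes the exposures: "Patients will receive two [¹⁴C]oxaliplatin microdose infusions over the course of the study". The first is given alone. For the second, two days to four weeks later, "The initial treatment oxaliplatin dose will be diluted with the same amount of [¹⁴C]oxaliplatin microdose as previously administered". The footnote to the regimen table in Section 6.5.2 confirms this: "Note during cycle 1 only, Oxaliplatin infusion will contain [¹⁴C]Oxaliplatin Microdose as described in section 6.4.1". If the label dose is titrated, Sections 3.1.3 and 6.3.2 assign the other dose levels to different patients.

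The nearest endpoint is 8.2.2.2: "Comparison of the PK parameters of the phase 0 microdose to the FOLFOX-integrated microdose". For it, Section 11.2.2.2 says "we will correlate PK parameters from phase 0 microdosing with parameters from FOLFOX-integrated microdosing of oxaliplatin", summarised by scatterplots, tables, means, SDs and a correlation coefficient. The 5% limit does not reappear in Section 8.2.2 or Section 11.

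**The concern.** Intrapatient variation of an exposure is what remains when the same patient receives the same thing again under the same conditions. Here the two occasions differ by design. The first is the microdose alone. The second is the same labelled amount inside a full oxaliplatin dose, given with the rest of FOLFOX. Order is fixed, so occasion and condition cannot be separated.

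The largest difference between the occasions is total dose, and its effect on dose-normalised AUC is what the primary endpoint (Section 8.2.1) sets out to learn. Reading the between-occasion difference as repeatability would assume the primary answer. The overlap is close: the only plasma assay described, in Sections 10.1.1 and 10.2.2, is ¹⁴C by liquid scintillation counting. As written, the FOLFOX-integrated microdose and the therapeutic dose are therefore measured by the same curve, and endpoints 8.2.2.1 and 8.2.2.2 rest on one contrast.

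At stake is what the study may say about the assay. A small real dose effect could be taken for poor repeatability, or a small difference called a validation of something that was not repeated.

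**Working it through.** **The plan's own figure.** Section 11.3 gives six patients for an 80% probability that the 95% CI of the full-dose to microdose geometric mean ratio lies within 0.5 to 2, with CVs of 0.3 to 0.5. The within-person correlation ρ is not stated. Take a true ratio of 1 and SD of the log ratio = √ln(1 + CV²) × √(2(1 − ρ)).
- CV 0.3, ρ = 0: SD = 0.2936 × 1.4142 = 0.415. The probability at n = 6 is 80.7%, so six is reproduced.
- CV 0.4 needs ρ of at least 0.41 for n = 6, and CV 0.5 needs at least 0.61. With ρ = 0 they need 9 and 12 patients.

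This calculation concerns a 2-fold range. No sample size or decision rule is given for the 5% objective.

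**Dose ratio between the occasions.** Inputs are the Section 6.3.1 example (1.7 m, 75 kg) and Table 1.
- BSA = 0.20247 × 1.7^0.725 × 75^0.425 = 1.86 m². Therapeutic dose = 85 × 1.8635 = 158.4 mg.
- Levels -1 and 1 (1%): microdose 1.58 mg, ratio 158.4/1.58 ≈ 100.
- Levels 2 and 3 (3%): microdose 4.75 mg, ratio 158.4/4.75 ≈ 33.

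**What two occasions can show.** Let D be a patient's difference in log dose-normalised AUC, σw the true within-patient SD, δ the systematic shift between conditions, and σI the SD of patient-specific shifts. If random variation is equal and independent on the two occasions:
- uncentred: E[D²]/2 = σw² + (δ² + σI²)/2
- mean removed: Var(D)/2 = σw² + σI²/2

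An SD s on the log scale converts to CV = √(exp(s²) − 1). One pair per patient cannot separate σw from the other terms.

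**Illustration, uncentred, with σw = σI = 0.** The choice of formula is an assumption, since the plan names none.
- Shift 7.3%: δ = ln 1.0732 = 0.0707, δ²/2 = 0.00250, CV = 5.0%.
- Shift 10%: δ = 0.0953, δ²/2 = 0.00454, CV = 6.7%.

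**Illustration, mean removed.** Assume a true CV of 3% and σI = 0.10. Then s² = ln(1.0009) + 0.10²/2 = 0.0009 + 0.0050 = 0.0059, and CV = 7.7%. Removing the average shift does not isolate repeatability.

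**Precision with six pairs (5 degrees of freedom, normal log ratios).** A CV of 5% corresponds to s = √ln(1.0025) = 0.0500.
- Observed 5%: 95% limits for s are 0.0500 × √(5/12.83) and 0.0500 × √(5/0.831), that is, a CV of 3.1% to 12.3%.
- For a one-sided 95% upper limit below 5%, the observed s must be at most 0.0500 × √(1.145/5) = 0.0239, a CV of about 2.4%.
- In the best case of six true replicate pairs, the chance of meeting that is 79% if the true CV is 2%, 53% at 2.5%, 33% at 3% and 12% at 4%. The true CVs are assumptions; the documents give none.

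**The case against.** The strongest reply is that the comparison is not empty. Total between-occasion variation contains the within-patient variation, so under the conditions given in the fix a total clearly below 5% would also place repeatability below 5%. This stands. A reader might infer that the objective cannot be answered at all. The documents do not support that: the information is one-sided, with a high total uninterpretable and a low total supportive but hard to reach with six patients. Sampling windows of ±10 to ±60 minutes at most time points (Table 2) will not help.

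Four other limits are fair.
- A reader might say that the second dose is always 100-fold larger. Table 1 sets total oxaliplatin at 3% for levels 2 and 3, so about 33-fold applies there.
- A reader might add biologic agents to the confounders. Section 4.1.3 allows them, but the study calendar, as extracted, places them at Cycle 1 Day 3, after nearly all of the sampling. Nor do the documents show that 5-FU, leucovorin or premedication alters oxaliplatin kinetics; Sections 3.1.2 and 3.2.3 describe non-enzymatic conversion without cytochrome P450 metabolism. The dose effect is the main confounder.
- The 7.3% and 10% figures depend on an uncentred CV. With the mean removed, a uniform shift contributes nothing and only patient-specific shifts matter.
- A reader might infer that the trial would declare the assay unrepeatable. No such decision exists: Section 11.2.2 treats all secondary analyses as exploratory, and the planned plots and means could reveal a systematic shift.

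The last reply does not rescue the objective. An exploratory status conflicts with an aim to validate against a fixed limit, and a correlation coefficient does not measure within-patient variation.

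**Conclusion.** The point holds. Objective 1.2.2 claims a property that this design does not test, because no patient has a second stand-alone microdose and nothing elsewhere in the documents supplies one. The between-occasion difference combines random variation, the dose effect under study in the primary endpoint, and any effect of FOLFOX co-administration.

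The size is material against a 5% limit. A 10% systematic shift, far inside the 2-fold margin of the primary criterion, would by itself exceed the limit on an uncentred CV. Patient-specific shifts of the assumed size would exceed it even after centring. Both are illustrations, since the plan gives neither a CV formula nor an expected dose effect. The precision figures assume six evaluable patients and normally distributed log ratios. The consequence concerns what may be concluded from a secondary objective; the primary criterion is unaffected.

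**What to change.** Reword 1.2.2, 8.2.2.2 and 11.2.2.2 to estimate the within-patient, between-occasion difference in dose-normalised AUC between the microdose alone and the microdose given with the therapeutic dose. Delete the word *validate* and the 5% limit. Report, each with a 95% CI:
- (a) the mean log ratio, as the systematic shift between the two conditions;
- (b) the SD of the log ratios divided by √2, described as total between-occasion variation.

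State that the upper confidence limit of (b), not its point estimate, may be read as an upper bound on intrapatient variation, and only if random variation is equal and independent on the two occasions. If equality is in doubt, (b) reflects an average over the two conditions, and the undivided SD with its upper limit is the conservative bound; it still needs independence. State plainly that repeatability of the microdose alone is not tested in this study.

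The cost is the text of one objective, one endpoint and one analysis paragraph. No infusion, sample or patient is added, and dosing is untouched. The reworded endpoint will overlap with 8.2.2.1 while both rest on the ¹⁴C curve, and the text should say so. The study gives up a claim of validated variation below 5%, which its design cannot support.

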2 BACKGROUND

The goal of this study is to test the feasibility of using microdose-based diagnostics in combination with oxaliplatin-based chemotherapy for personalized cancer treatment. The key hypotheses are that the intravenous infusion of a microdose of [¹⁴C]oxaliplatin (~1% of the therapeutic dose) will 1) predict the pharmacokinetic exposure to treatment dose oxaliplatin and 2) that accumulation of the microdose-induced oxaliplatin-DNA damage in surrogate genomic DNA from peripheral blood mononuclear cells (PBMCs) will correlate with patient response to subsequent full-dose oxaliplatin-based chemotherapy. In this study, our main objective is to collect enough data to evaluate the feasibility of using a [¹⁴C]oxaliplatin microdose as a clinical assay to predict oxaliplatin exposure. Key secondary objectives are to assess oxaliplatin-DNA adduct biomarkers in PBMCs and assess intrapatient variability of microdose pharmacokinetics. Since there will be less than a hundred oxaliplatin-DNA adducts per genome, an ultrasensitive measurement technology is required. Accelerator mass spectrometry (AMS) is the most sensitive method available for precise and accurate measurement of drug-DNA adducts. AMS requires a rare isotope label, such as radiocarbon (¹⁴C). For this study we will be dosing patients with sub-therapeutic nontoxic doses of ¹⁴C-labeled oxaliplatin ([¹⁴C]oxaliplatin) that will result in minimal radiation exposure to patients (less than one chest X-ray of radiation exposure per microdose).

2.1 Overview of Cancer Treatment with Platinum Agents

Platinum (Pt) derivatives are among the most effective and commonly used chemotherapeutic drugs for lung, bladder, breast, gynecological, gastrointestinal, testicular, hematological and other malignancies. Three platinum-based drugs, cisplatin, carboplatin and oxaliplatin, are used for chemotherapy in the U.S. The pharmacodynamic mechanism of platinum chemotherapy is the formation of covalent platinum-DNA adducts (**Figure 1**).

[figure not shown]
[figure not shown]

Figure 1. Structure of oxaliplatin and formation of oxaliplatin-DNA adducts. The ¹⁴C label (*) is covalently linked to DNA in both oxaliplatin-DNA monoadducts and diadducts. Only when adducts are repaired is the ¹⁴C label removed from DNA. AMS measures ¹⁴C and, therefore, both monoadducts and diadducts in genomic DNA. By measuring the decrease of ¹⁴C from genomic DNA, the rate of removal of DNA monoadducts and diadducts (DNA repair) can be measured.

Platinum-based drugs preferentially interact with the nucleophilic N7-site of purine bases of DNA to form a variety of monoadducts and diadducts (crosslinks) when Pt interacts with nucleotides through one or two bonds, respectively [1]. Both intrastrand and interstrand diadducts occur in DNA. The structures of these adducts are well characterized. These adducts induce local perturbations in the DNA double helical structure, which activate the proteins that recognize DNA damage [2-4]. The activation of these proteins also results in cell cycle arrest, induction of DNA repair processes, and the initiation of programmed cell death (**Figure 2**). Although many details of the mechanisms of action have yet to be elucidated, the binding of Pt agents to DNA is well known and is the underlying basis for measuring Pt-DNA adducts in cells as a potential predictor of patient response to platinum-based chemotherapy. Moreover, the efficacy of platinum-based chemotherapy varies significantly depending on the types of cancer and individual molecular characteristics. For example, most testicular cancer patients respond to and can be cured with platinum-based chemotherapy regimens like BEP (bleomycin, etoposide and cisplatin), even in the presence of distant metastasis. Platinum-based chemotherapy for other types of cancer is less effective.

2.2 Oxaliplatin

Oxaliplatin is the third generation of platinum compounds approved for use in cancer therapy. It differs from cisplatin and carboplatin in two significant ways. First, oxaliplatin's toxicity profile shows a reduction in renal and auditory toxicities, and minimal myelosuppression. And second, it does not share the same resistance spectrum as of cisplatin and carboplatin. Oxaliplatin is active in many solid tumors, including colorectal, pancreatic, ovarian, lung, and head and neck carcinomas. Oxaliplatin is presently approved for use in combination with 5-fluorouracil (5-FU) and leucovorin (folic acid). This treatment regimen is indicated for (1) adjuvant treatment of stage III colon cancer in patients who have undergone complete resection of the primary tumor and (2) advanced colorectal cancer, (3) gastroesophageal adenocarcinoma, (4) pancreatic adenocarcinoma, (5) biliary adenocarcinoma, (6) appendiceal adenocarcinoma, (7) duodenal adenocarcinoma. At the present time, the most commonly used combination (modified FOLFOX6) combines oxaliplatin with bolus leucovorin and 5-FU followed by a 46-hour infusion of 5-FU [5, 6].

Oxaliplatin-associated toxicities are cumulative with dose received and are the most frequent cause of withdrawal from therapy for those patients that respond well to FOLFOX. The major dose limiting toxicity of oxaliplatin is neurotoxicity, which results in treatment interruption and discontinuation prior to disease progression in the majority of patients [7]. The predictability of neurotoxicity associated with oxaliplatin-based therapy should allow the development of strategies to manage this side effect in view of the individual patient's clinical situation. Variation of oxaliplatin in individual patients could affect the accumulation

of oxaliplatin with the nervous system as well as the disposition of oxalate. Thus, oxaliplatin dose optimization has the potential to reduce the development of neurotoxicity in patients treated with FOLFOX.

In phase I studies, the calculated exposure or area under the curve (AUC) of oxaliplatin administered at 85 mg/m² averaged 4.68 µg/mL/hr; however, there was significant inter-patient variation in AUC (SD 1.40 µg/mL/hr). The metabolism of oxaliplatin occurs in a triphasic manner. The initial ($T_{1/2\alpha}$), second ($T_{1/2\beta}$) and terminal ($T_{1/2\gamma}$) phase half-lives of oxaliplatin are reported to be 25.8 minutes, 16.8 hours and 391 hours, respectively [8, 9]. Approximately half of oxaliplatin is excreted in urine within the first 6 hours. Only a small fraction of oxaliplatin is excreted at the terminal phase. Because the formation of Pt-DNA adducts correlated to the concentration and incubation time of cells with Pt [10], and because there is a linear correlation between gross levels of platinum bound to DNA and the extent of cytotoxicity [11], it is conceivable that those patients with longer serum half-life of Pt may have more cytotoxic effects. We hypothesize that increased metabolism (short half-life) may be responsible for some cases of resistance to Pt agents. Therefore, a PK study may identify those patients with a short half-life of Pt and help design personalized therapy studies altering the dose of oxaliplatin to overcome resistance.

